4.3.1.4 Dates for Medications

In case of (partially) missing start and end dates of concomitant medications and non-drug therapies, the dates will be imputed so that the extent of exposure to the concomitant medication/non-drug therapy is maximal:

- Missing start day will be imputed as the first day of the month.

- Missing end day will be imputed as the last day of the month.
- Missing start month will be imputed as the first month of the year (January).
- Missing end month will be imputed as the last month of the year (December).

4.4 Study Patients

4.4.1 Disposition of Patients

Disposition of patients will be based on the ES.

The number and percentage of patients enrolled, screened, dosed, completed or prematurely discontinued the study including primary reason for discontinuation will be presented by treatment group and total. Percentages will be based on the number of patients in the ES.

A by-patient listing of disposition will be presented including date of informed consent, date/time of first and last study drug, study completion status and date of completion/ premature discontinuation with primary reason for discontinuation.

In case of interim analyses, the status will include ongoing for patients enrolled, but not completed or discontinued.

Reasons for screen failure will be listed for patients failing screening.

4.4.2 Protocol Deviations

Important protocol deviations (IPDs) are defined as those deviations from the protocol likely to have an impact on the perceived efficacy of study drug. The impact of IPDs on efficacy results will be investigated by assessing the robustness of the study results and conclusions to the choice of analysis set, both including and excluding data potentially affected by IPDs.

This evaluation of importance will be completed before database lock and resulting residence of patients in each analysis set confirmed and approved by the Sponsor. The final confirmation is planned to be performed within the Data Review Meeting minutes signed prior to database lock. During study conduct, regular protocol deviation reviews will be performed, which allow assigning an action for analysis “Exclude from Per Protocol Set (PPS) Analysis”, which will be used to identify IPDs.

The major/minor protocol deviations and default action to be taken regarding the exclusion of subjects or affected data from specific analyses are defined in the project-specific Protocol Deviation Specification, but can differ from the classification as IPD.

Any major protocol deviations as well as all IPDs (if different) will be listed and the number and percentage of patients with IPDs summarized by type of deviation based on the Treated Set.

4.5 Analysis Sets

Enrolled Set (ES)	All patients who signed informed consent. The ES will be used for patient disposition information.
Entered Subjects	All subjects of the ES who have a pre-treatment assessment of any impulsivity test or questionnaire (This includes subjects who are not treated).
Treated Set (TS)	All subjects who were treated with at least one dose of study drug (i.e. placebo or atomoxetine). The TS will be used for safety analysis.
Treated Set 1 (TS1)	All subjects who were treated at Day 1 with one dose of study drug (i.e. placebo or atomoxetine). The TS1 will be used for the primary analysis at Day 1.
Treated Set 14 (TS14)	All subjects in the TS who were treated according to protocol for at least 90% (not more than one missed dose) of the planned doses of study drug (i.e. placebo or atomoxetine). The TS14 will be used for the primary analysis at Day 14. Please see Section 4.9.2 for definition of treatment compliance.
Per Protocol Set (PPS)	All subjects of the TS which have no IPDs. The PPS will be used for sensitivity analysis of efficacy.
Pharmacokinetic Per Protocol Set (PK-PPS)	The PK-PPS includes all subjects from the TS who provide at least one PK value that was not excluded due to a protocol deviation relevant to the evaluation of PK.

A summary of the number and percentage of patients in each analysis set will be presented for the ES, with denominators based on the number of patients who were enrolled.

A by-patient listing of analysis set details will be presented for all enrolled patients, including the patient identifier, site and indication of inclusion into/exclusion from each analysis set.

Upon database release, protocol deviation and analysis set outputs will be produced and will be sent to Boehringer Ingelheim for review. An analysis population classification meeting will be arranged to discuss the outputs and to decide which subjects and/or subject data will be excluded from certain analyses (especially for the set PK-PPS but not limited to this set). Decisions made regarding the exclusion of subjects and/or subject data from analyses will be documented and approved by Boehringer Ingelheim.

If a subject is allocated the incorrect study drug as per the study randomisation list, subjects will be analyzed 'as treated' i.e. by actual treatment group for all outputs as follows. Identification of such cases will be confirmed and documented in the Data Review Meeting minutes.

- TS1: Subjects will be counted towards the treatment arm as treated regardless of their randomisation.

CONFIDENTIAL

Project Document Version No. 2.0

Effective Date: 30 Jan 19

Project Document Effective Date: Date of last signature

Related to: [REDACTED]

Page 18 of 41

- TS14: In the rare case of partial mistreatment (both atomoxetine and placebo), the patient will be part of TS14 only if either more than 90% of the received doses are atomoxetine or more than 90% of the received doses are placebo. Percentages less than 90% will lead to exclusion from TS14 (as the compliance is less than 90%).
- TS: In the rare case of partial mistreatment (both atomoxetine and placebo), the patient will be analyzed as belonging to the atomoxetine arm for all safety analyses.

4.6 Demographics and Baseline Characteristics

Demographics and baseline characteristics will be listed by patient and summarized descriptively by treatment group and total using the TS. This includes age at screening, sex, ethnicity, race, highest level of education at screening, and status of employment at screening. Birth year will only be listed.

If the subject has consumed alcohol in the past 3 months (Yes/No) and if the subject consumed tobacco (current/previous/never) will be summarized by counts and percentage relative to the number of subjects in the TS.

Detailed alcohol and smoking history information will only be listed.

4.7 Medical History and Concomitant Illnesses

Medical history and concomitant illnesses, i.e. medical conditions with an onset date earlier than the screening visit date and end date either before screening visit (medical history) or still ongoing at time of screening (concomitant illness).

These medical conditions are collected via the eCRF and then coded using MedDRA version 24.1 or higher.

All related medical history will be listed including description of the disease/procedure, MedDRA SOC, PT, start date and stop date (or ongoing, if applicable). Number of subjects with a history or concomitant illness will be counted by SOC and PT and by treatment group. Percentages will be based on the number of subjects in the TS.

4.8 Prior and Concomitant Medications

Medication taken before and during the study are collected in the eCRF and coded according to ATC classification of the WHODD January 2022 or later.

Medication start and stop dates will be compared to the date of Visit 2 to allow medications to be classified as either Prior only, both Prior and Concomitant, or Concomitant only. Medications captured that start after the treatment completion/withdrawal date will be listed but will not be classified or summarized.

- Medications that start and stop prior to the date of Visit 2 will be classified as Prior only.

CONFIDENTIAL

Project Document Version No. 2.0

Effective Date: 30 Jan 19

Project Document Effective Date: Date of last signature

Related to: [REDACTED]

Page 19 of 41

- If a medication starts before the date of Visit 2 and stops on or after the date of Visit 2, then the medication will be classified as both Prior and Concomitant.
- Medications will be classified as Concomitant only if they have a start date on or after the date of Visit 2, but not after the last dose of study drug.

If medication start and/or stop dates are missing or partial, the dates will be compared as far as possible with the date of first dose of study drug. Medications will be assumed to be Concomitant only, unless there is clear evidence (through comparison of partial dates) to suggest that the medication started prior to Visit 2. If there is clear evidence to suggest that the medication started prior to Visit 2, the medication will be assumed to be both Prior and Concomitant, unless there is clear evidence to suggest that the medication stopped prior to Visit 2. If there is clear evidence to suggest that the medication stopped prior to Visit 2, the medication will be assumed to be Prior only.

The duration of the medication will be calculated as:

$$\text{Duration} = (\text{end date}) - (\text{start date}) + 1$$

The TS will be used for listing and summary of prior and concomitant medication. The patient data listing and summary table will include the anatomical main group (level 1), the therapeutic subgroup (level 2), preferred name and reported term. Counts and percentages of subjects taking medication for each of these levels will be based on the number of subjects in the TS.

4.9 Treatment Exposure / Compliance

4.9.1 Treatment Exposure

The study drug administration dates and times for site treatment visits will be listed for each participant for the planned administration visits together with administered number of capsules as documented in the study drug administration eCRF.

Additionally, daily intake of the study drug is monitored using a smartphone app serving as a reminder to the subjects for intake of the medication. Each pill intake is planned to be captured with date and time.

A subject level listing will be created for the TS to present both eCRF and e-diary information of study drug intake. This listing will include the number of pills administered at treatment visits (eCRF), date and time of each intake documented in the e-diary, total number of pills taken per subject as well as the number of actual days of study drug intakes, the number of planned days of study drug intakes and the treatment compliance percentage (per Section 4.9.2).

The total number of pills taken per subject as well as the treatment compliance percentage will be summarized by treatment group for the TS.

4.9.2 Compliance

The study drug is to be taken once daily in either 80 mg or 40 mg doses. Subject compliance to study drug will be evaluated as percentage of missed dosing days determined by e-diary data for

CONFIDENTIAL

Project Document Version No. 2.0

Effective Date: 30 Jan 19

Project Document Effective Date: Date of last signature

Related to: [REDACTED]

Page 20 of 41

drug intake monitoring at home. The number of planned days of study drug intake is 14 days for all patients. Partial intake of study drug (e.g. 40 mg instead of 80 mg) will be counted as compliant.

$$\text{Treatment compliance (\%)} = \frac{\text{number of actual days of study drug intakes}}{\text{number of planned days of study drug intakes}} * 100$$

4.10 Endpoint Evaluation

4.10.1 Analysis and Data Conventions

Analyses on the primary, secondary, and further exploratory endpoints will be conducted in an exploratory way and therefore no formal statistical hypothesis testing is planned in this study and no formal sample size calculations (see Section 4.12) were performed.

4.10.1.1 Multi-center Studies

All sites (i.e. investigational sites) will be combined together for the purposes of the analysis.

4.10.1.2 Handling of Dropouts or Missing Data

Dropouts will be defined as patients who prematurely discontinue from the study and study drug at the same time for any reason. This also includes patients who are lost to follow-up.

Handling of missing data due to dropout is described in Sections 4.10.1.6 and 4.10.3 for efficacy variables, no action for missing data due to dropouts is taken for other variables. Patients who dropped out will not be excluded from any summaries, except where clearly stated.

4.10.1.3 Multiple Comparisons/Multiplicity

Given that

- No formal hypothesis testing is planned and
- The study has an exploratory nature

No adjustments for multiplicity and methods for controlling the Type I error are required.

4.10.1.4 Interim Analyses

No formal interim analysis will be performed and therefore no methods for controlling the Type I error are required. No formal interim clinical trial report is planned.

The following preliminary, exploratory, and non-decisional analyses may be performed:

- A first preliminary exploratory analysis of the primary and further efficacy endpoints might be performed when approximately 60% of patients will have completed treatment (i.e. Visit 4 - Day 14 – end of treatment) and will include all efficacy data. The cut-off date will be the date on which the 48th patient (i.e. 60% of 80 evaluable patients) completes Visit 4.
- A second preliminary exploratory analysis of the primary and further efficacy endpoints may be performed when the last patient will complete treatment (i.e. Visit 4 - Day 14 –

CONFIDENTIAL

Project Document Version No. 2.0

Effective Date: 30 Jan 19

Project Document Effective Date: Date of last signature

[figure not shown]
Related to: [REDACTED]

Page 21 of 41

end of treatment) and will include all efficacy data. The cut-off date will be the date on which the last patient completes Visit 4.

- Preliminary exploratory analysis of PK concentrations of atomoxetine may be performed based on all evaluable data prior to data base lock. This may be necessary e.g. to confirm treatment compliance and appropriateness of measurements for primary analysis and/or, if required, to inform other investigations in development. In contrast to the final PK calculations, the preliminary, exploratory analysis may be based on planned sampling times rather than on actual times, regardless of whether actual times were within the time windows or not. Therefore, minor deviations of preliminary and final results may occur. No formal preliminary PK report will be written. This analysis of PK data may be standalone or combined with one of the other analyses.

The cut-off dates will be the same for all patients. A database snapshot will be taken with regard to these cut-off dates, including all efficacy data available in the database up to the cut-off date, and will be used for analysis purpose. Only cumulative results will be presented, i.e. patient level and safety data will be excluded. Investigators (outcome assessors) and everyone involved in trial conduct (except the trial personnel involved in the administering the trial medication—third-party blinding) will remain blinded and will not have access to the unblinded snapshot data. Trial functions of the sponsor and responsible global vendor are unblinded (including CTL/PM, data managers, statisticians, bioanalysts, pharmacokineticists, pharmacometrists) and will conduct all interim analyses.

4.10.1.6 Vomiting and Nausea

Cases of vomiting and nausea can occur following intake of atomoxetine. Vomiting and nausea events will be captured as AEs and the sites / patients will be encouraged to report start and end times of these events to identify impact on study drug as well as impulsivity testing. Such AEs will be summarized separately (please refer to Section 4.11.1).

If the start time of the AE of vomiting or nausea is missing, it will be assumed not to have affected treatment or impulsivity assessment.

On Day 1 and Day 14, occurrence of vomiting post-dose, but before PK sampling will lead to exclusion of any following PK sample from summary statistics (see Section 4.10.5) for the PK concentrations of that day. E.g., if vomiting occurs on Day 14 post-dose, but before the first sampling time on Day 14, both Day 14 samples (pre- and post-impulsivity testing) will be excluded from PK summaries. Such events will be reviewed during AE review and the preliminary and/or interim analysis or at the Data Review Meeting prior to database lock.

 CONFIDENTIAL

Project Document Version No. 2.0

Effective Date: 30 Jan 19

Project Document Effective Date: Date of last signature

Related to: 

Page 22 of 41

It is expected that vomiting and nausea can have influence on the conduct of impulsivity assessments. For the primary analysis, occurrence of these events will not lead to exclusion from the analysis and this event is handled by the treatment policy strategy.

4.10.2 Primary Endpoints

4.10.2.1 Change from Baseline in Total Score of Barratt Impulsiveness Questionnaire v.11 After Single Dose (at Day 1)

All analyses described below for the primary efficacy variables will be analyzed on the TS1 by randomized treatment arm, regardless of any changes to dose interval.

The estimand is specified through the following definitions of population, variable, treatment condition, ICE, and population-level summary:

Population: Defined by the inclusion/exclusion criteria.

Variable: Absolute change from baseline to Day 1 in total score of BIS-11 questionnaire.

The Barratt Impulsiveness Scale is a questionnaire designed to assess the personality/behavioral construct of impulsiveness. It is composed of 30 items/questions describing common impulsive or non-impulsive (for reverse scored items) behaviors and preferences. Items are scored on a 4-point scale from “1” for the least impulsive choice to “4” for most impulsive choice (i.e. Rarely/Never = 1; Occasionally = 2; Often = 3; Almost Always/Always = 4). The total score is given by the sum of the scores of the single items, thus ranging from 30 (minimum score – most favorable score) to 120 (maximum score – least favorable score).

Treatment condition: Atomoxetine arm vs. placebo arm.

Intercurrent events (ICE): Premature discontinuation from treatment: While-on-treatment strategy. Only assessments prior to the occurrence of the intercurrent event will be considered.

Use of concomitant/rescue therapy: Treatment policy strategy. The occurrence of the intercurrent event is considered irrelevant in defining the treatment effect of interest: the value for the variable of interest is used regardless of whether or not the intercurrent event occurs.

Vomiting or nausea: Treatment policy strategy. The estimate is accepted to include occurrences of this intercurrent event: the value

CONFIDENTIAL

Project Document Version No. 2.0

Effective Date: 30 Jan 19

Project Document Effective Date: Date of last signature

Related to: [REDACTED]

Page 23 of 41

for the variable of interest is used regardless of whether or not the intercurrent event occurs.

Death: Composite strategy. It is not expected that there will be any death during the study but if any death occurs it will be handled with a composite strategy where the worst possible outcome (i.e. maximum score of 120) will be used in the analysis.

Population-level summary: Difference in mean change from baseline to Day 1 in total score of BIS-11 between Atomoxetine arm and placebo arm.
Negative differences favor the atomoxetine arm.

4.10.2.2 Change from Baseline in Total Score of Barratt Impulsiveness Questionnaire v.11 at Steady State (at Day 14)

All analyses described below for the primary efficacy variables will be analyzed on the TS14 by randomized treatment arm, regardless of any changes to dose interval.

The estimand is specified through the following definitions of population, variable, treatment condition, intercurrent events, and population-level summary:

Population: Defined by the inclusion/exclusion criteria.

Variable: Absolute change from baseline to Day 14 in total score of BIS-11 questionnaire.

See above for details on BIS-11 questionnaire and total score.

Treatment condition: Atomoxetine arm vs. placebo arm.

Intercurrent events (ICE): Premature discontinuation from treatment: While-on-treatment strategy. Only assessments prior to the occurrence of the intercurrent event will be considered.

Use of concomitant/rescue therapy: Treatment policy strategy. The occurrence of the intercurrent event is considered irrelevant in defining the treatment effect of interest: the value for the variable of interest is used regardless of whether or not the intercurrent event occurs.

Vomiting or nausea: Treatment policy strategy. The estimate is accepted to include occurrences of this intercurrent event: the value for the variable of interest is used regardless of whether or not the intercurrent event occurs.

Death: Composite strategy. It is not expected that there will be any death during the study but if any death occurs it will be handled with a composite strategy where the worst possible outcome (i.e. maximum score of 120) will be used in the analysis.

Population-level summary: Difference in mean change from baseline to Day 14 in total score of BIS-11 between Atomoxetine arm and placebo arm.
Negative differences favor the atomoxetine arm.

4.10.2.3 Change from Baseline in Total Score of S-UPPS-P Impulsive Behavior Scale After Single Dose (at Day 1)

All analyses described below for the primary efficacy variables will be analyzed on the TS1 by randomized treatment arm, regardless of any changes to dose interval.

The estimand is specified through the following definitions of population, variable, treatment condition, intercurrent events, and population-level summary:

Population: Defined by the inclusion/exclusion criteria.

Variable: Absolute change from baseline to Day 1 in total score of S-UPPS-P Impulsive Behavior Scale questionnaire.

The S-UPPS-P Impulsive Behavior Scale is a questionnaire designed to assess impulsivity as a multi-faceted and multi-dimensional construct, comprising five impulsive personality traits. It is composed of 20 items/questions describing impulsive or non-impulsive (for reverse scored items) behavior. Items are scored on a 4-point scale from “1” for the least impulsive choice to “4” for most impulsive choice (i.e. Agree Strongly = 1; Agree Some = 2; Disagree Some = 3; Disagree Strongly = 4). The total score is given by the sum of the scores of the single items, thus ranging from 20 (minimum score – most favorable score) to 80 (maximum score – least favorable score).

Treatment condition: Atomoxetine arm vs. placebo arm.

Intercurrent events (ICE): Premature discontinuation from treatment: While-on-treatment strategy. Only assessments prior to the occurrence of the intercurrent event will be considered.

Use of concomitant/rescue therapy: Treatment policy strategy. The occurrence of the intercurrent event is considered irrelevant in defining the treatment effect of interest: the value for the variable of interest is used regardless of whether or not the intercurrent event occurs.

Vomiting or nausea: Treatment policy strategy. The estimate is accepted to include occurrences of this intercurrent event: the value for the variable of interest is used regardless of whether or not the intercurrent event occurs.

CONFIDENTIAL

Project Document Version No. 2.0

Effective Date: 30 Jan 19

Project Document Effective Date: Date of last signature

Related to: [REDACTED]

Page 25 of 41

Death: Composite strategy. It is not expected that there will be any death during the study but if any death occurs it will be handled with a composite strategy where the worst possible outcome (i.e. maximum score of 80) will be used in the analysis.

Population-level summary: Difference in mean change from baseline to Day 1 in total score of S-UPPS-P Impulsive Behavior Scale between atomoxetine arm and placebo arm.
Negative differences favor the atomoxetine arm.

4.10.2.4 Change from Baseline in Total Score of S-UPPS-P Impulsive Behavior Scale at steady state (at Day 14)

All analyses described below for the primary efficacy variables will be analyzed on the TS14 by randomized treatment arm, regardless of any changes to dose interval.

The estimand is specified through the following definitions of population, variable, treatment condition, intercurrent events, and population-level summary:

Population: Defined by the inclusion/exclusion criteria.

Variable: Absolute change from baseline to Day 14 in total score of S-UPPS-P Impulsive Behavior Scale questionnaire.

See above for details on S-UPPS-P questionnaire and total score.

Treatment condition: Atomoxetine arm vs. placebo arm.

Intercurrent events (ICE): Premature discontinuation from treatment: While-on-treatment strategy. Only assessments prior to the occurrence of the intercurrent event will be considered.

Use of concomitant/rescue therapy: Treatment policy strategy. The occurrence of the intercurrent event is considered irrelevant in defining the treatment effect of interest: the value for the variable of interest is used regardless of whether or not the intercurrent event occurs.

Vomiting or nausea: Treatment policy strategy. The estimate is accepted to include occurrences of this intercurrent event: the value for the variable of interest is used regardless of whether or not the intercurrent event occurs.

Death: Composite strategy. It is not expected that there will be any death during the study but if any death occurs it will be handled with a composite strategy where the worst possible outcome (i.e. maximum score of 80) will be used in the analysis.

CONFIDENTIAL

Project Document Version No. 2.0

Effective Date: 30 Jan 19

Project Document Effective Date: Date of last signature

Related to: [REDACTED]

Page 26 of 41

Population-level summary: Difference in mean change from baseline to Day 14 in total score of S-UPPS-P Impulsive Behavior Scale between atomoxetine arm and placebo arm.
Negative differences favor the atomoxetine arm.

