5.1 ASSESSMENT OF EFFICACY

S-UPPS-P Impulsive Behavior Scale Urgency, Perseverance, Premeditation, and Sensation Seeking – Positive Urgency

The S-UPPS-P is a shortened version of the original UPPS-P (Urgency, Perseverance, Premeditation, and Sensation Seeking – Positive Urgency) impulsive behavior scale that has been developed and validated as a reliable alternative to the full version ([R19-3281](#)).

The S-UPPS-P is comprised of 20 items, 4 items specifically selected from each of the 5 pathways. The first pathway, Urgency, assesses an individual's tendency to give in to strong impulses, specifically when accompanied by negative emotions such as depression, anxiety, or anger. The next pathway, (lack of) Perseverance, assesses an individual's ability to persist in completing jobs or obligations despite boredom and/or fatigue. The third pathway, (lack of) Premeditation, assesses an individual's ability to think through the potential consequences of his or her behavior before acting. The fourth pathway, Sensation Seeking, measures an individual's preference for excitement and stimulation. And the final pathway, Positive Urgency, assesses an individual's tendency to give in to strong impulses, when accompanied by positive emotions such as excitement or good mood.

Each item on the S-UPPS-P is rated on a 4-point scale ranging from 1 (Strongly Agree) to 4 (Strongly Disagree).

The S-UPPS-P Impulsive Behavior Scale ranges from 20 to 80 with a higher score indicating an increased impulsive behavior.

[figure not shown]
The S-UPPS-P is to be completed by the patient and should take approximately 8-10 minutes to complete. The S-UPPS-P will be captured using the rater station/tablet provided by the vendor.

[figure not shown]
Barratt Impulsiveness Questionnaire v.11 (BIS-11) [[R06-1093](#)]

BIS-11 is a widely used self-report measure of impulsiveness. It includes 30 items that are scored to yield six first-order factors (attention, motor, self-control, cognitive complexity, perseverance, and cognitive instability impulsiveness) and three second-order factors (attentional, motor, and non-planning impulsiveness).

The total BIS-11 score ranges from 30 to 120 with a higher score indicating an increased impulsive behavior.

BIS-11 is to be completed by the patient and should take approximately 20 minutes to complete. The BIS-11 will be captured using the rater station/tablet provided by the vendor.

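### The S-UPPS-P response key and reversal rule in SAP 4.10.2.3 contradict its stated direction; applied as printed, they reverse the sign of two of the four primary endpoints

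*SAP*

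**What the plan says.** SAP 4.10.2.3 defines the S-UPPS-P total through three statements.

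- **Reversal:** "It is composed of 20 items/questions describing impulsive or non-impulsive (for reverse scored items) behavior". The non-impulsive items are thus the reversed ones.
- **Direction:** 1 is the least impulsive choice and 4 the most. The total is a plain sum with a top value of "80 (maximum score – least favorable score". For the treatment contrast, "Negative differences favor the atomoxetine arm".
- **Key:** the direction is then spelled out as 4 "for most impulsive choice (i.e. Agree Strongly = 1; Agree Some = 2; Disagree Some = 3; Disagree Strongly = 4".

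SAP 4.10.2.4 takes the same scoring to Day 14: "See above for details on S-UPPS-P questionnaire and total score".

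Protocol 5.1 gives the response format, "Each item on the S-UPPS-P is rated on a 4-point scale ranging from 1 (Strongly Agree) to 4 (Strongly Disagree", and the direction, "The S-UPPS-P Impulsive Behavior Scale ranges from 20 to 80 with a higher score indicating an increased impulsive behavior". It does not say which items are reversed. It adds that "The S-UPPS-P will be captured using the rater station/tablet provided by the vendor", but not whether the export holds raw responses or scored items.

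**The concern.** The key is offered as the meaning of the direction but says the opposite. The BIS-11 sentence in SAP 4.10.2.1 has the same construction and is consistent, because its anchors run from rarely or never (1) to almost always or always (4), so a high code on an impulsive item does mean more impulsive. With an agreement scale that starts at 1 for strong agreement, the same reversal rule turns the scale round.

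The two S-UPPS-P endpoints are read on the rule that a negative difference is a benefit, so a reversed total would report a benefit as harm. Beside a correctly scored BIS-11, S-UPPS-P would appear to move the other way, in a trial whose main objective is to identify the best-suited impulsivity measures. The optional preliminary analyses in SAP 4.10.1.4 cover the same endpoints.

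**Working it through.** **Inputs.** From SAP 4.10.2.3: 20 items, each scored 1 to 4, raw code r running from strong agreement (1) to strong disagreement (4), non-impulsive items reversed. From SAP 4.10.2.5: ANCOVA of change from baseline on baseline score and arm.

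**The plan's own range.** 20 × 1 = 20 and 20 × 4 = 80, as stated. Both scorings below give this range.

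**Item level.**

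| Item wording | Response | Raw r | Score under stated direction | Score under printed key and reversal |
|---|---|---|---|---|
| Impulsive | Strong agreement | 1 | 5 − 1 = 4 | 1 |
| Impulsive | Strong disagreement | 4 | 5 − 4 = 1 | 4 |
| Non-impulsive | Strong agreement | 1 | 1 | 5 − 1 = 4 |
| Non-impulsive | Strong disagreement | 4 | 4 | 5 − 4 = 1 |

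If s is the intended item score, the printed rule gives 5 − s for every item.

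**Total.** The sum of (5 − s) over 20 items is 100 − S, where S is the intended total. The number of impulsive-worded items does not enter. Simulated response sets for every split from 0 to 20 gave exactly 100 − S each time. The most impulsive pattern scores 20 instead of 80, and the least impulsive 80 instead of 20.

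**Treatment effect.** Let B be the baseline total and P the post-baseline total. The change becomes (100 − P) − (100 − B) = −(P − B), and the covariate becomes 100 − B. Substituting into the ANCOVA gives treatment coefficient −μ, the same baseline slope and the same residual variance.

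A simulated data set confirmed this (40 per arm; assumed baseline mean 52 and SD 8, residual SD 5, true effect −3). The difference was −2.37 (95% CI −4.57 to −0.18) with intended scoring and +2.37 (0.18 to 4.57) with the printed rule. SE (1.10) and p (0.034) were the same under both.

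**Illustration of size.** Assume a true difference of −4.0, 40 per arm and a common residual SD; neither the difference nor the SDs are in the documents. Half-width = t(0.975, 77) × SD × √(2/40).

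| Residual SD (assumed) | Half-width | Intended 95% CI | Printed rule 95% CI |
|---|---|---|---|
| 5 | 2.23 | −6.2 to −1.8 | +1.8 to +6.2 |
| 7 | 3.12 | −7.1 to −0.9 | +0.9 to +7.1 |
| 10 | 4.45 | −8.5 to +0.5 | −0.5 to +8.5 |

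**Key applied with no reversal.** With k impulsive-worded items, the most impulsive pattern sums to 80 − 3k and the least impulsive to 20 + 3k. At an assumed k = 12 these are 44 and 56. This total is a mixture of right-way and wrong-way items, not a mirror image.

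**Death rule.** The imputed 80 is the best score on the reversed scale. A patient with intended baseline 52 would have a change of 80 − 52 = +28. On the reversed scale the baseline is 48 and the change 80 − 48 = +32, where an exact mirror would be −28.

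**The case against.** The intended direction is not in doubt. The anchors, the favourable and unfavourable ends of the total, the death value and the reading rule all agree with Protocol 5.1, and SAP section 1 makes the protocol govern unless the SAP explicitly says otherwise. Only one parenthesis points the other way, and it looks like the raw response format placed in the BIS-11 sentence. The remark about reversed items is descriptive, so a programmer would have to consult the instrument's key, which should settle direction. If the vendor exports scored items, nothing flips. An item list may sit in SAP appendices that were not available for this review. The trial is exploratory, outputs are independently checked, and raw responses survive, so an error could be corrected by reprogramming.

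Much of this stands. The sign reversal is one conditional path, the documents do not show which path will be programmed, and no stated rule makes agreement in direction with BIS-11 a criterion for choosing measures. But none of it removes a wrong key from a primary-endpoint definition. An appendix would add a further instruction without reconciling the text. Exploratory status does not help either, since the estimate with its sign and interval is what these endpoints deliver.

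**Conclusion.** The concern holds. SAP 4.10.2.3 contains incompatible scoring instructions, and following the printed key with the printed reversal gives exactly 100 minus the intended total. Two of the four primary endpoints (S-UPPS-P at Day 1 and Day 14) would then have the opposite sign; BIS-11 is unaffected. Absolute effect size, SD, interval width and two-sided p-value are unchanged, so the error is one of direction only.

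The algebra needs no assumption about item wording. It needs both the key and the reversal to be applied as printed, and the exact mirror image also requires that no death is imputed (none is expected). The −4.0 difference and the SDs are illustrative. Because one of the two readings reverses the conclusion, the text must be corrected before the score is derived for any analysis.

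**What to change.** In SAP 4.10.2.3, state that raw responses are coded from 1 (strong agreement) to 4 (strong disagreement), that impulsive-worded items are scored as 5 minus raw, that non-impulsive-worded items keep the raw code, and that a higher total means more impulsive. List the recoded items by number from the instrument's own key. State whether the vendor tablet exports raw or already scored values, so that no item is recoded twice.

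Before analysis, confirm direction, for example by checking that baseline S-UPPS-P and BIS-11 totals correlate positively. With 80 patients (Fisher z), a fully reversed score would still show a positive sample correlation with probability 3.8%, 0.33% or below 0.001% if the true correlation is 0.2, 0.3 or 0.5 (assumed range). The check is not reliable for partial mis-keying, so it does not replace the item list.

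Add one matching sentence to Protocol 5.1 when the protocol is next amended; the SAP correction alone is enough to protect the analysis. The cost is SAP wording, one derivation program and that sentence, with no change to data collection.
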